### 6.2 Enrollment/Baseline Visit (Visit 1, Day 0)

- Review and confirm informed consent.
- Verify inclusion/exclusion criteria.
- Update any changes in demographic information, medical/dental history, medication history, alcohol and tobacco use history.
- Record results of physical and dental examinations.
- Collect blood/urine/saliva/other specimen.
- A single blood sample will be collected via antecubital venipuncture by a phlebotomist prior to MR imaging, 10-15 ml blood collected. The blood sample will be collected after verification of negative urine pregnancy test in women of childbearing potential.
- All patients will undergo a comprehensive baseline clinical assessment including evaluation of their cardiovascular risk factor profile. The specific information that will be collected is seen in the table below.

Table 2: Clinical Assessment Parameters to be Collected

Demographics	Antecedent CV Hx & Risk Factors	Clinical Parameters	Current Medications	Clinical Biochemistry	Ultrasound Findings
Age-Years Sex-% male Race Body Mass Index – kg/m  Alcohol use Tobacco Use	Smoking T2D Hypertension Hypercholesterolemia	Heart Rate Systolic BP Diastolic BP Ankle-brachial index	Aspirin Clopidogrel Statin blocker ACE/ARI Calcium channel blocker Other anti-hypertensives Oral nitrates	Total Cholesterol HDL-C, LDL-C VLDL Triglycerides Creatinine BUN AST ALT Bilirubin hsCRP Uric Acid Salivary cortisol	Thickness of anterior and distal wall of artery with lesion. Assessment of flow restriction

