### 8.1 Aim I

The first study aim is to estimate the bias and precision of each of the following functional analytes, which will be measured for each target lesion by both vascuCAP™ and histopathology:

- a. Plaque lipid
- b. Plaque fibrosis
- c. Plaque inflammation
- d. Intra-plaque hemorrhage burden and confidence.
- e. Plaque vascular leak
- f. Calcification

For each of these functional analytes, three measurements will be evaluated for a total of 18 measurements per target lesion: volume in mm^3, and degree and uniformity both measured on a three-point ordinal scale. The same measurements will be taken via histopathology, where the volume of each analyte will be measured using the same units (i.e. mm^3); however, degree and uniformity are graded subjectively on histopathology by the pathologist.

We anticipate that each patient will have at least one target lesion and some patients, especially the PAD patients, will have two target lesions, on average. There will be no replicate measurements (i.e. all of the measurements are obtained objectively by the algorithm so multiple runs should not produce different results).

For volume measurements for each analyte for each site (i.e. neck and leg), we will plot the value measured by histopathology vs. the difference between the value measured by vascuCAP™ and the value measured by histopathology. Any analyte not measurable will also be indicated on the plot using a different plotting character. The resulting plot will be inspected visually for the following:

1. Limits of vascuCAP™'s quantitation;
2. Associations between the magnitude of the histopathology measurement and bias; and
3. Associations between the magnitude of the histopathology measurements and heteroscedasticity in the vascuCAP™ measurements.

If the plots of carotid and femoral endarterectomies have similar distributions, then the data from these sites will be pooled; otherwise, separate analyses will be performed.

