A linear model will be fit (for all of the data or for a subset of histopathology values, depending on the findings from the plot) where the dependent variable is the vascuCAP™ measurement ( $X$ ) and the independent variable is the histopathology value ( $Y$ ). Generalized estimating equations (GEEs) (to account for the fact that some patients will have more than one target lesion) will be used to estimate the linear function:  $E(Y|X) = \beta_0 + \beta_1 X$ . An unstructured working covariance will be used. We will construct a 95% CI for the intercept  $\beta_0$  using a t-statistic as the pivotal statistic. CIs not containing 0 indicate fixed bias. We will also construct a 95% CI for the slope  $\beta_1$ . CIs not containing 1 indicate proportional bias [11].

The precision of the vascuCAP™ measurements will be estimated by the standard deviation:

$$\sqrt{\frac{1}{n-1} \sum_{i=1}^n (Y_i - X_i - \bar{d})^2} \text{ where } \bar{d} \text{ is the sample mean of the differences, } \bar{d} = \frac{1}{n} \sum_{i=1}^n (Y_i - X_i) \text{ [1].}$$

We will construct a 95% CI for the precision using bootstrap methods.

We will plot the bias profile (plot of bias of measurements for various ranges of histopathology values vs. the histopathology value) and precision profile (plot of standard deviation of vascuCAP™ measurements from patients with similar histopathology values vs. the histopathology value) as visual summaries of vascuCAP™ performance for the bias and precision components, respectively [12].

In addition to reporting these technical performance characteristics of the volume measurements, we will also report i) the coverage probability (CP) and ii) a discrimination index [11]. The CP is the probability that the absolute difference between the value measured by vascuCAP™ and the value measured by histology is less than  $d_0$ , i.e.  $\pi = \Pr(|Y - X| < d_0)$ . We will plot the CP for a range of values for  $d_0$ . The discrimination ability of the measurements, i.e. the ability of vascuCAP™ to discriminate between different magnitudes of histopathology values, will be measured using the area under the ROC curve for continuous measures [13]. 95% CIs for the CP and ROC area will be constructed using methods for clustered binary data [14] and clustered ROC data [15], respectively.

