**Table 5: Estimated 95% CIs for SD Based on Total Sample Size (n)\***

	n=10	n=20	n=30	n=40	n=50	n=60
SD=2.5	[1.80,4.77]	[1.98,3.81]	[2.08,3.51]	[2.11,3.29]	[2.16,3.20]	[2.19,3.14]
SD=3.75	[2.70,7.16]	[2.97,5.71]	[3.11,5.26]	[3.17,4.94]	[3.24,4.80]	[3.29,4.71]
SD=5.0	[3.60,9.54]	[3.96,7.61]	[4.15,7.02]	[4.22,6.59]	[4.31,6.40]	[4.38,6.29]

\*The effective sample size,  $m$ , is calculated as  $m=(3/4)n+(1/4)n(2/[1+(s-1)0.5])$ , where  $s=2$ .

Then the 95% CI for the SD is  $[\sqrt{\frac{(m-1)s^2}{\chi_{\frac{\alpha}{2},(m-1)}^2}}, \sqrt{\frac{(m-1)s^2}{\chi_{(1-\frac{\alpha}{2}), (m-1)}^2}}]$ .

For degree and uniformity measurements for each analyte for each site (i.e. neck and leg), we will tabulate the histopathology value vs. the vascuCAP™ value. Any analyte not measurable will also be indicated in the table. In the distributions in the tables are similar, then the data from the two sites will be pooled.

The coverage probability (CP) will be reported which is the probability that the absolute difference between the value measured by vascuCAP™ and the value measured by histology is less than  $d_0$ , i.e.  $\pi = \Pr(|Y - X| < d_0)$ . We will report the CP for values for  $d_0$  of 0 and 1. 95% CIs for the CP will be constructed using methods for clustered binary data [6].

For volume, degree, and uniformity of the six functional analytes, we will estimate the reproducibility of the measures at different institutions (two sites), and under different scanner models and field strengths (1.5 and 3.0) and with respect to ranges documented in the literature according to collected patient characteristics. Multiple variable linear and logistic regression models will be built, where the dependent variable is the difference between the measured functional analyte and the true value, and the independent variables are institution, scanner model, field strengths, and patient characteristics. We will test whether the independent variables in the model are predictors of bias using F-tests, and Wald tests, respectively.

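### The reproducibility regressions for the functional analytes omit the histology value (and vascular bed once beds are pooled), so unequal case mix can create or hide an apparent site, scanner or field-strength bias

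*Combined protocol and SAP*

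**What the plan says.** Reproducibility of the functional analytes is part of primary objective I (section 3.1). Section 8.1 addresses it in one paragraph, after Table 5. The aim is to estimate "reproducibility of the measures at different institutions (two sites), and under different scanner models and field strengths (1.5 and 3.0" tesla, as I read the unit). The outcome and first covariates are given as "where the dependent variable is the difference between the measured functional analyte and the true value, and the independent variables are institution, scanner model", and the list ends with "field strengths, and patient characteristics". The use is inferential: "We will test whether the independent variables in the model are predictors of bias using F-tests, and Wald tests, respectively". No alpha or acceptance limit is given.

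Patient characteristics are not defined there. The nearest list is Table 2 in section 6.2 ("The specific information that will be collected is seen in the table below"), which contains neither the histology value nor the vascular bed.

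Earlier in section 8.1 the plan allows for bias that depends on lesion size. The difference plots are inspected for "Associations between the magnitude of the histopathology measurement and bias", and for the slope of vascuCAP on histology, "CIs not containing 1 indicate proportional bias". The sample-size text adds that bias and precision may have to be stratified by histology volume, anatomic location or both. Carotid and femoral data are pooled only if their distributions look alike. Besides volume, each analyte has "degree and uniformity both measured on a three-point ordinal scale".

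**The concern.** When bias depends on lesion size, the mean difference in any group of lesions depends on the sizes in that group. Patients are not randomised to hospitals or scanners; they are recruited where they are scheduled for imaging and surgery. A comparison of mean differences between platforms therefore mixes device behaviour with case mix unless the histology value is in the model. Vascular bed acts in the same way after pooling.

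On the 0/1/2 scales the dependence is close to structural: a true 0 can only be misread upward and a true 2 only downward. A logistic model is also named for an outcome that can take five values (−2 to 2), with no dichotomy or ordinal form given.

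These are the only stated comparisons of functional-analyte performance across hospitals, scanners and field strengths, and section 4 says the phase-two data go into the 510(k) application.

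**Working it through.** **Plan's own figure, as a yardstick.** No sample size or power is stated for these regressions. The nearest figure is the bias CI at n=35, SD 15%. By the Table 4 footnote, m = 0.75×35 + 0.25×35×(2/1.5) = 37.9, and the half-width is 2.026×3.75/√37.9 = ±1.23 mm³. The total width is 2.47/25 = 9.9%, which agrees with the stated 10%.

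**Inputs from section 8.1.** Mean volume 25 mm³; SD 10–20% of that, with 3.75 used here; phase-two minimum 25 + 10×2 = 45 lesions; phase one 55 + 20×2 = 95 lesions; within-patient correlation 0.5.

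**Assumptions not in the documents.** Two-sided 5% test; slopes 0.8–1; gaps in mean histology volume of 0–10 mm³; between-lesion volume SD 12.5 mm³; lesions split 23 v 22 (or 48 v 47) and independent unless stated; misgrading rates; bed imbalance.

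**Volumes.** Write V for the vascuCAP value and H for histology. If V = b0 + b1·H + error, then V − H = b0 + (b1 − 1)·H + error. With H omitted and no true institution effect:

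- expected institution contrast = (b1 − 1) × gap in mean H
- residual SD = √(3.75² + (b1 − 1)²×12.5²)
- SE at 45 lesions = residual SD × √(1/23 + 1/22) = residual SD × 0.298

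| Slope | Gap (mm³) | False shift (mm³) | SE | False-flag rate, 45 lesions |
|---|---|---|---|---|
| 1.0 | 10 | 0 | 1.12 | 5% |
| 0.8 | 0 | 0 | 1.34 | 5% |
| 0.9 | 5 | −0.5 | 1.18 | 7% |
| 0.9 | 10 | −1.0 | 1.18 | 13% |
| 0.8 | 10 | −2.0 | 1.34 | 31% (28–31% across simulations) |

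The last shift is 2/25 = 8% of the mean volume and exceeds the ±1.23 mm³ half-width. With H in the model the rate is about 5% in every row. At 95 lesions, simulation with a volume SD of 10 gave 61% for slope 0.8 and gap 10.

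**Masking.** Take slope 0.8, gap 10 and a real +2 mm³ institution effect. The planned contrast is 2 − 2 = 0, so it is flagged only 5% of the time. With H in the model the estimate is 2.0 mm³, with SE 3.75×√(1/23 + 1/22 + 100/(43×156.25)) = 1.21, and it is flagged about 37% of the time.

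**Vascular bed, if pooled.** Suppose bias differs by 2.5 mm³ between beds, and one hospital has 65% of the carotid and 25% of the PAD patients. At 45 lesions its femoral share is 5/21.25 = 24%, against 15/23.75 = 63% at the other. The false shift is about 0.40×2.5 = 1.0 mm³, flagged 14% of the time (23% at 95 lesions). With bed in the model it is 4–5%.

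**Grades.** Let a fraction e be misgraded by one step, identically at both hospitals, with true 1 split evenly up and down. The mean difference is +e, 0, −e for true grades 0, 1, 2. Grade mixes of 50/30/20% and 20/30/50% give means of +0.3e and −0.3e, so the false difference is 0.6e, with variance e − (0.3e)² in each group.

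| e | False difference (grade) | False flags, 45 lesions | 95 lesions |
|---|---|---|---|
| 20% | 0.12 | 13–14% | 24–26% |
| 30% | 0.18 | 19% | 36% |

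With histology grade as a factor, both fall to about 4–5%.

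**Clustering.** With lesion correlation 0.5, ordinary least squares that ignores clustering rejects 6.5–8% of the time even after adjustment for H and bed.

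**The case against.** Much of the case on the other side stands.

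- **The error is conditional.** A reader might infer that ordinary case-mix differences will be reported as platform bias. The documents do not support that: bias must vary with volume or bed, and the mix must differ between groups. They predict neither a slope of 0.8 nor a 10 mm³ gap, and phase one allows the software to be revised before lock, so an early slope need not persist. A more extreme example, means of 15 v 35 mm³, is flagged about 82% of the time, but that gap is 80% of the assumed mean volume and is not ordinary case mix.
- **Bed is partly handled** by the pool-or-separate rule. The gap is confined to pooled data, where the decision to pool is visual.
- **Proportional bias is examined elsewhere**, by plot, slope CI, bias profile and possible strata. None of these carries the histology value into the reproducibility regressions.
- **Table 2.** A reader might infer that all of its roughly 37 items enter one model fitted to as few as 35 patients. The plan does not say so; it leaves patient characteristics undefined.
- **Adjustment has a price.** H is part of the outcome, so error in H couples the two. With slope 1, and SD 3.75 split equally between device and histology, the adjusted model gives a false shift of (1 − reliability) × gap. For a 10 mm³ gap this is 0.043×10 = 0.4 mm³ at volume SD 12.5, and 0.111×10 = 1.1 mm³ at SD 7.5; the unadjusted model has none. The plan treats histology as truth, so adjustment fits its own framework, but this deserves a sensitivity analysis.
- **Precision.** The gain from adding H exists only when the slope is not 1.

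**Conclusion.** The concern holds in conditional form. The model for the difference leaves out a variable on which the plan itself expects bias to depend, and leaves out bed after pooling. For volumes the consequence runs from nothing (slope 1 or equal mix) to a 2 mm³ false shift flagged in roughly three trials in ten (slope 0.8, gap 10 mm³, 45 lesions), and a real effect of similar size can be hidden. For grades the first condition is nearly built in, so unequal grade mix alone is enough. All rates rest on the assumed slopes, gaps, volume SD, misgrading rates and 5% level; the algebra does not.

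This is a should-fix. The tests inform a primary objective, but they carry no acceptance limit and do not drive the sample size, which rests on the interval widths in Tables 4 and 5.

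**What to change.** Amend the final paragraph of section 8.1:

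1. Include the histology value in every reproducibility model, and vascular bed whenever beds are pooled.
2. For degree and uniformity, replace the logistic model of the difference with a cumulative-logit model of the vascuCAP grade, with histology grade as a factor.
3. Use GEE or cluster-robust standard errors for patients with two lesions, in line with the main Aim I analysis.
4. Define patient characteristics, and label these and any histology-by-platform interactions exploratory.
5. Report the model without the histology value as a sensitivity analysis, because adjustment relies on histology being the truth standard.

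The cost is SAP wording and one to three model degrees of freedom. The histology value and vascular bed are already available for every lesion analysed.

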The volume measurements are considered the most critical because they will be used to construct a score to predict rupture risk. Thus, we considered the width of 95% confidence intervals for the bias and the between-subject variance as a function of sample size (see Tables 1 and 2). The following assumptions were made: 1) the volume measurements are normally distributed; 2) carotid artery patients contribute one target lesion each, while PAD patients contribute two target lesions each; 3) target lesions from the same patient are moderately correlated ( $r=0.5$ ); 4) one-quarter of all patients will be PAD patients; 5) results from femoral and carotid target lesions can be pooled; 6) the average volume of an analyte is  $25\text{mm}^3$ ; and 6) the precision of the vascuCAP™ measurements is 10-20% of the volume of analyte.

From Table 4, if the SD was 15% of the mean volume, then we expect to be able to construct a 95% CI for the bias of total width of 10% with  $n=35$ . If the SD was 20%, then with  $n=35$  we expect to construct a 95% CI of total width of 14%. Similarly, from Table 5, if the SD was 15% of the mean volume, then with  $n=35$  we expect to be able to construct a 95% CI for the precision of total length 8%; if the SD was 20%, then we expect to be able to construct a 95% CI for the precision of total length 11%. We plan to recruit 75 patients (55 carotid artery patients and 20 PAD patients) in phase one to account for the fact that the estimates of bias and

precision may need to be reported in strata based on the magnitude of the histopathology volume and/or by anatomic location. In phase two we plan to recruit at least the minimum of 35 (25 carotid artery patients and 10 PAD patients) and possibly more depending on the results of the training set.

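### The Aim I reproducibility regressions name no adjustment for two correlated lesions per PAD patient, and promise tests but no confidence intervals for site, scanner and field-strength effects

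*Combined protocol and SAP*

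**What the plan says.** The last paragraph of Section 8.1 (after Table 5) covers volume, degree and uniformity of the six functional analytes. Its aim is estimation: "we will estimate the reproducibility of the measures at different institutions (two sites), and under different scanner models and field strengths". Its method is: "Multiple variable linear and logistic regression models will be built, where the dependent variable is the difference between the measured functional analyte". The comparator is the histopathology result, and the predictors are institution, scanner model, field strength and patient characteristics. Its inference is: "We will test whether the independent variables in the model are predictors of bias using F-tests, and Wald tests, respectively". It names no cluster adjustment and no interval.

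Elsewhere Section 8.1 treats lesions from one patient as correlated:

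- It expects that "some patients, especially the PAD patients, will have two target lesions, on average".
- The precision calculation assumes that "carotid artery patients contribute one target lesion each, while PAD patients contribute two target lesions each" and that "target lesions from the same patient are moderately correlated", with r = 0.5. Tables 4 and 5 therefore use an effective sample size.
- The regression of bias on volume uses GEE "to account for the fact that some patients will have more than one target lesion".
- The ROC area, and the coverage probability for volume, get clustered-data methods. For degree and uniformity, "95% CIs for the CP will be constructed using methods for clustered binary data".

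Each of these provisions is tied to its own estimand, and none is extended to the reproducibility models. In Section 8.2, Aim II examines the same three factors and does commit to bootstrap intervals for the differences between their levels.

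**The concern.** Each patient has one study MRI, so institution, scanner model and field strength take the same value for both lesions of a PAD patient. An ordinary lesion-level regression counts those two lesions as independent evidence on a patient-level factor, and its standard error is too small. Followed as written, the volume models would flag site or scanner effects that do not exist more often than the nominal rate.

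The second gap is in reporting. Reproducibility is part of primary objective I, and phase-two results go into the 510(k) report. A test says whether a difference was detected, not how large a difference the data leave open. With 35 patients, a non-significant result could be read as reproducibility when it only reflects low precision.

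**Working it through.** **Inputs from Section 8.1.** Phase two minimum: 25 carotid + 10 PAD patients. Phase one: 55 + 20. One lesion per carotid patient, two per PAD patient, r = 0.5. Mean volume 25 mm³; SD of differences 2.5, 3.75 or 5.0 mm³ (10%, 15%, 20%).

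**Assumptions not in the documents.** Two-sided 5% tests (no level is stated) and an even split of patients between institutions.

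**1. The plan's own figure.** At n = 35, m = (3/4)(35) + (1/4)(35)(2/1.5) = 37.92. Half-width = 2.032 × 3.75/√37.92 = 1.24 mm³, so the total width is 2.475/25 = 9.9%. The text says 10%. It reproduces, with clustering counted.

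**2. Variance inflation for a patient-level factor.** D = [carotid + 2 × PAD × (1 + r)] / lesions, and true error = 2[1 − Φ(1.96/√D)].

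- 25 + 10: D = (25 + 30)/45 = 1.222, √D = 1.106; error 7.6%.
- 55 + 20: D = (55 + 60)/95 = 1.211; error 7.5%.
- Femoral only: D = 1.5; error 11.0%.
- Carotid only: D = 1; error 5%.

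**3. Simulation of the unadjusted linear-model test** (one factor, exchangeable correlation, 200,000 runs): 7.7% (25 + 10), 7.5% (55 + 20), 11.7% and 11.2% (10 and 20 femoral patients), 5.1% (25 carotid). Independent shorter runs gave 7.4-7.9% pooled. For r = 0.3 to 0.7 the pooled range across runs is about 6.4-8.9%. If only half of the PAD patients have two lesions, it is 6.4% and 6.3%.

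**4. Remedies for the volume models** (20,000 runs for the adjusted methods). The six-parameter model has an intercept, institution, scanner model, field strength and two patient characteristics. Scanner is 70% concordant with institution, and field strength with scanner (assumed).

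| Method | One factor, 25+10 | One factor, 55+20 | Six parameters, 25+10 | Six parameters, 55+20 |
|---|---|---|---|---|
| Unadjusted | 7.7% | 7.5% | 7.7% | 7.5% |
| Cluster-robust CR1, t on patients | 5.6% | 5.2% | 7.4% | 6.4% |
| Cluster-robust CR2, t on patients | 5.4% | 5.1% | 6.3% | 5.9% |
| CR2, Satterthwaite df | not run | not run | 5.1% | 5.4% |
| Patient random intercept (REML), t | 5.4% | 5.0% | 5.1% | 5.2% |

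At n = 35 with several covariates, CR1 with a simple t reference repairs almost nothing.

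**5. Logistic branch, unadjusted Wald test** (one factor, latent r = 0.5; the agreement rates are assumed). At 25 + 10: 5.7% with 70% agreement and about 2% with 85%. At 55 + 20: about 6.3% and 4.6%. The error depends on the agreement rate and can fall below 5%. No remedy was simulated for this branch.

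**6. What an interval would show.** For a two-institution difference at 25 + 10, m = 25 + 10(2/1.5) = 38.33. With SD 15%, half-width = 2.026 × 3.75 × √(4/38.33) = 2.45 mm³ = 9.8% of 25. Scaling by SD gives 6.5% at SD 10% and 13.1% at SD 20%. An 80:20 split multiplies these by 2.5/2 = 1.25, so 9.8% becomes 12.3%. At n = 75 (m = 81.67) it is 1.65 mm³ = 6.6%. In the six-parameter model the mean half-width is 0.773 SD (n = 35) and 0.495 SD (n = 75), or 11.6% and 7.4% at SD 15%. Power at n = 35 to detect a true 10% shift, with one factor and SD 15%, is about 52-54%.

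**The case against.** **This is an omission, not a prohibition.** Section 8.1 shows that its authors know about clustering, and nothing bars an adjustment. That stands, and an oversight is the likely explanation. But F-tests from ordinary regression are what the paragraph specifies, and an analyst following it would fit independent rows. The contrast with the rest of the plan should not be overdrawn either: the bootstrap interval for the precision SD and the Aim II bootstrap also name no patient-level resampling.

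**The inflation covers a minority of outcomes.** A reader might infer that all 18 measurements are affected. They are not shown to be. Six are volumes. The other twelve are ordinal grades, the natural targets of the logistic models, where the unadjusted Wald test can be conservative. This objection holds.

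**The interval is a reporting preference.** The paragraph does promise estimation, and Aim II uses a different statistic, so its intervals do not make Aim I inconsistent. That is fair. The case for intervals rests on the precision figures in step 6, not on the comparison with Aim II.

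**The consequences are small.** Six volumes by three factors give 18 tests: 18 × 0.05 = 0.9 false flags expected at the nominal rate, against 18 × 0.077 = 1.4. Spurious flags also count against the device rather than for it. Both points are true of the tests. An interval from the unadjusted fit, however, would be too narrow, which errs the other way.

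**The logistic outcome.** It is tempting to read it as exact agreement, using the coverage-probability event with d₀ = 1. The documents do not settle this. With the strict inequality as printed, the d₀ = 0 event is impossible, so a non-strict one may have been meant, and d₀ = 1 would then mean within one grade. Exact agreement would also merge over-grading with under-grading, while these models are about bias.

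**Conclusion.** Wrong as written, with minor to moderate weight. For the volume outcomes, the unadjusted test of institution, scanner model or field strength has a true type I error of about 7.5-8% when carotid and femoral lesions are pooled (about 6.4-8.9% for r = 0.3 to 0.7). It is about 11-12% if femoral lesions are analysed separately, and there is no inflation for carotid lesions alone. For degree and uniformity no inflation is claimed.

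These figures rest on the plan's two lesions per PAD patient and r = 0.5, and on the assumed 5% level and even split. Fewer second lesions would lower them. The lack of a promised interval matters at least as much: at n = 35 and SD 15%, a non-significant test is compatible with an institution difference of roughly 10% of the mean volume.

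A reader might go further and infer that the plan's primary conclusions or its sample size are compromised. The documents do not support that, because no success rule and no sample-size calculation uses these tests.

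**What to change.** In the last paragraph of Section 8.1:

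1. Fit the volume models with patient as the cluster. Use either a mixed model with a patient random intercept and a t reference based on the number of patients, or GEE/cluster-robust standard errors with the CR2 correction and Satterthwaite degrees of freedom. Do not rely on CR1 with a simple t reference.
2. Fit the degree and uniformity models by a method that also accounts for clustering by patient.
3. Report the estimated effect of institution, scanner model and field strength with a 95% confidence interval as the main reproducibility result, with the F or Wald test as a supplement.

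The cost is a few sentences in the plan and a few lines of code, with no extra patients. The downside is honest but wider uncertainty: standard errors for these factors become about 10% larger pooled, and about 25% larger femoral-only, than the unadjusted ones.
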